Redacted	

#### 4.8.4 Safety

The safety of MEDI3902 will be analysed through 49 days postdose in the As-treated Population.

#### 4.8.4.1 Analysis of Adverse Events

[figure not shown]
Safety of MEDI3902 will primarily be assessed and measured by the occurrence of all TEAEs and TESAEs.

- Occurrence of AEs through 49 days postdose
- Occurrence of SAEs through 49 days postdose
- Occurrence of AESIs to include targeted AEs of hepatic function abnormalities, hypersensitivity reactions (including anaphylaxis), infusion related reactions, and immune complex disease (eg, vasculitis, endocarditis, neuritis, glomerulonephritis) through 49 days postdose

Adverse events and SAEs will be summarised by Medical Dictionary for Regulatory Activities system organ class and preferred term, and by severity and relationship to investigational product.

#### 4.8.4.2 Analysis of Clinical Laboratory Parameters

Clinical laboratory measurements (ie, serum chemistry, and hematology) will be summarised from baseline through 21 days postdose.

#### 4.8.6 Pharmacokinetics

Individual MEDI3902 concentrations in serum will be tabulated for all subjects by treatment group along with descriptive statistics through 49 days postdose.

Noncompartmental PK data analysis will be performed for MEDI3902 data obtained from treatment group with scheduled PK sample collection where data allows. Relevant descriptive statistics of noncompartmental PK parameters for MEDI3902 will be provided and may include AUC, Cmax, clearance, and half-life and Vdss.

#### 4.8.7 Anti-drug Antibody Response

The immunogenic potential of MEDI3902 will be assessed by summarising the number and percentage of subjects who develop detectable ADAs in serum through 49 days postdose. The impact of ADA on PK will be assessed if data allow. Safety data will also be assessed in subjects with ADA.

Reda	
R e	
e	
Redacted	

#### 4.8.10 Data Review Committees

Safety data will be reviewed regularly by the sponsor and an independent DMC. Efficacy data will be assessed by a blinded independent adjudication committee.

#### **Data Monitoring Committee**

An independent DMC will review safety data regularly and make recommendations regarding further study conduct. The DMC will also be responsible for recommending dose adjustment as outlined in Section 4.8.11. Further details will be provided in the DMC charter.

#### Adjudication Committee

A blinded independent endpoint adjudication committee will review clinical, radiographic, and microbiologic data for adjudication of efficacy endpoints and may request to review all data relevant to a potential case, including any radiographic and imaging studies performed for medical management of a subject, and any other clinical and/or microbiologic data as deemed relevant by the adjudication committee.

#### 4.8.11 Interim Analysis

An interim PK data analysis will be performed after at least 10 subjects in each of the mg MEDI3902 and placebo groups are followed through 21 days postdose. The interim PK analysis will allow the determination of serum PK profile of MEDI3902 in mechanically ventilated subjects. Enrolment will continue in both the mg MEDI3902 and placebo groups while the PK interim analysis is conducted. An independent DMC will be responsible for recommending dose adjustment as outlined in the following criteria: If the mean serum concentration of MEDI3902 on Day 22 in the mg MEDI3902 dose group is lower than

the target concentration of  $\frac{Re}{da}$  µg/mL, a dose adjustment to  $\frac{Reda}{da}$  mg MEDI3902 will be considered.

## 4.8.12 Planned Analysis

A blinded sample size re-estimation will be performed after approximately 50% of subjects have been followed through 21 days postdose, as described in Section 4.8.2. A final analysis will be performed after all subjects have completed the study.

# 5 ASSESSMENT OF SAFETY

# 5.1 Definition of Adverse Events

The ICH Guideline for Good Clinical Practice E6(R1) defines an AE as:

Any untoward medical occurrence in a patient or clinical investigation subject administered a pharmaceutical product and which does not necessarily have a causal relationship with this treatment. An AE can therefore be any unfavorable and unintended sign (including an abnormal laboratory finding), symptom, or disease temporally associated with the use of a medicinal product, whether or not considered related to the medicinal product.

An AE includes but is not limited to any clinically significant worsening of a subject's preexisting condition. An abnormal laboratory finding (that requires medical intervention by the investigator, or a finding judged by the investigator as medically significant should be reported as an AE. If clinical sequelae are associated with a laboratory abnormality, the diagnosis or medical condition should be reported (eg, renal failure, hematuria) not the laboratory abnormality (eg, elevated creatinine, urine RBC increased). Abnormal laboratory values that are not, in the investigator's opinion, medically significant and do not require intervention should not be reported as AEs.

Adverse events may be treatment emergent (ie, occurring after initial receipt of investigational product) or nontreatment emergent. A nontreatment-emergent AE is any new sign or symptom, disease, or other untoward medical event that begins after written informed consent has been obtained but before the subject has received investigational product.

Elective treatment or surgery or preplanned treatment or surgery (that was scheduled prior to the subject being enrolled into the study) for a documented pre-existing condition that did not worsen from baseline is not considered an AE (serious or nonserious). An untoward medical event occurring during the prescheduled elective procedure or routinely scheduled treatment should be recorded as an AE or SAE.

# 5.2 Definition of Serious Adverse Events

An SAE is any AE that:

- Results in death
- Is immediately life-threatening
- Requires inpatient hospitalisation or prolongation of existing hospitalisation

- Results in persistent or significant disability/incapacity
- Is a congenital anomaly/birth defect in offspring of the subject
- Is an important medical event that may jeopardise the subject or may require medical intervention to prevent one of the outcomes listed above

Medical or scientific judgment should be exercised in deciding whether expedited reporting is appropriate in this situation. Examples of medically important events are intensive treatment in an emergency room or at home for allergic bronchospasm, blood dyscrasias, or convulsions that do not result in hospitalisations; or development of drug dependency or drug abuse.

# 5.3 Definition of Adverse Events of Special Interest

An AESI is one of scientific and medical interest specific to understanding of the investigational product and may require close monitoring and rapid communication by the investigator to the sponsor. An AESI may be serious or non-serious. The rapid reporting of AESIs allows ongoing surveillance of these events in order to characterise and understand them in association with the use of this investigational product.

## 5.3.1 Hepatic Function Abnormality

Hepatic function abnormality meeting the definition of Hy's law is considered an AESI. See Section 5.4.3.1 for the definition and reporting of AESIs of hepatic function abnormality.

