# 2.2 Study Endpoints

#### 2.2.1 Primary Endpoint

Efficacy of MEDI3902:

1. Incidence of nosocomial pneumonia caused by P aeruginosa through 21 days postdose

Safety of MEDI3902:

1. Treatment-emergent AEs (TEAEs), treatment-emergent SAEs (TESAEs) and AESIs through 49 days postdose

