#### 5.4.3.1 Hepatic Function Abnormality

Events of hepatic function abnormality, as defined in Section 5.3.1, should be recorded according to the definitions of AE and SAE (Section 5.1 and Section 5.2 respectively)

- If the underlying diagnosis for hepatic function abnormality is known (including progression of pre-existing disease), the diagnosis should be recorded as an AE or SAE per 5.4 or Section 5.5 respectively.
- If the underlying diagnosis for the hepatic function abnormality remains unknown, the term "hepatic function abnormal" should be used to report the AE or SAE per Section 5.4 or Section 5.5, respectively.

Medications used to treat these events should be recorded.

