### **Definitions**

# Potential Hy's Law (PHL)

Aspartate Aminotransferase (AST) or Alanine Aminotransferase (ALT)  $\geq$  3x Upper Limit of Normal (ULN) **together with** Total Bilirubin (TBL)  $\geq$  2xULN at any point during the study following the start of study medication irrespective of an increase in Alkaline Phosphatase (ALP).

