### Hy's Law (HL)

AST or  $ALT \ge 3x$  ULN **together with** TBL  $\ge 2x$ ULN, where no other reason, other than the IMP, can be found to explain the combination of increases, eg, elevated ALP indicating cholestasis, viral hepatitis, another drug.

For PHL and HL the elevation in transaminases must precede or be coincident with (i.e. on the same day) the elevation in TBL, but there is no specified timeframe within which the elevations in transaminases and TBL must occur.

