3.8.2 Adverse Events of Special Interest

Adverse events of special interest (AESI) will include targeted AEs of hypersensitivity (including anaphylaxis), infusion-related reactions, hepatic function abnormalities, and immune complex disease (eg, vasculitis, endocarditis, neuritis, glomerulonephritis, serum sickness, arthralgias) and will be summarized by treatment group and for MEDI3902 total

overall, and by SOC and PT based on MedDRA. Additional groupings may be added by the Medical Monitor if warranted.

An additional table will summarise duration and time to onset from dosing start for AESIs including hypersensitivity reactions, infusion related reactions and anaphylactic reactions.

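### The hepatic AESI counts only liver abnormalities with no cause found other than study drug; add a by-arm table of the combined laboratory elevation irrespective of cause, and settle which events count

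*Protocol*

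**What the plan says.** Protocol 2.2.1 gives the primary safety endpoint as "Treatment-emergent AEs (TEAEs), treatment-emergent SAEs (TESAEs) and AESIs through 49 days postdose".

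For the liver, Protocol 5.3.1 says "Hepatic function abnormality meeting the definition of Hy's law is considered an AESI" and then "See Section 5.4.3.1 for the definition and reporting of AESIs of hepatic function abnormality". Section 5.4.3.1 opens with "Events of hepatic function abnormality, as defined in Section 5.3.1". Its first recording branch reads: "If the underlying diagnosis for hepatic function abnormality is known (including progression of pre-existing disease), the diagnosis should be recorded as an AE or SAE". Its second branch gives a general hepatic term for use when the diagnosis remains unknown.

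Appendix 9 has two tiers with the same thresholds, AST or ALT at least 3 times ULN together with total bilirubin at least 2 times ULN:

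- **Potential Hy's Law** is the laboratory pattern after the start of study medication, with no condition on cause.
- **Hy's Law** is that pattern "where no other reason, other than the IMP, can be found to explain the combination of increases". The investigator and sponsor representatives agree on this for each case.

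On the analysis side, SAP 3.8.2 lists "hepatic function abnormalities, and immune complex disease" among the AESIs, with no laboratory threshold and no mention of Hy's Law. Protocol 4.8.4.1 is similarly broad. SAP 3.8.4 summarises laboratory parameters by treatment group: observed values, change from baseline, worst toxicity grade, Grade 3-4 frequencies, and shifts of two or more grades.

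**The concern.** A randomised, placebo-controlled comparison does not need a causal verdict on each subject; the difference between arms supplies it. Making the AESI conditional on attribution gives that up for the liver. Ventilated ICU patients often have a competing explanation for abnormal liver tests. If MEDI3902 raised the frequency of combined transaminase and bilirubin elevation, some or all of the extra cases could be attributed individually to other causes and drop out of the hepatic AESI count.

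The second issue is that the sections do not agree on the set being counted. Two programmers reading 5.3.1 with Appendix 9, or SAP 3.8.2 alone, could build different hepatic AESI tables from the same database.

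**Working it through.** The plan states no hepatic event rate or count, so there is no figure to reproduce. The check sets the texts side by side.

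1. **Who is in the set.** By Appendix 9, Hy's Law cases are the Potential Hy's Law cases minus those with an agreed other explanation. Under 5.3.1 the hepatic AESI count can therefore lie anywhere from zero to the full Potential Hy's Law count, depending only on the causality judgement.

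2. **Where the definition sits.** Section 5.3.1 sends the reader to 5.4.3.1 for it, and 5.4.3.1 sends the reader back. Neither gives laboratory criteria; the criteria and the causality condition are in Appendix 9.

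3. **The known-diagnosis branch.** Section 5.4.3.1 applies to events as 5.3.1 defines them. An event with a known other cause cannot be Hy's Law, so its first branch is empty under that definition.

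4. **Reporting terms.** Section 5.4.3.1 uses a general hepatic term, as AE or SAE. Appendix 9 requires an SAE under the term Hy's Law with causality set to related. For this category, the SAP 3.8.1 count of product-related AESIs then carries no separate information.

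5. **Where explained cases go.** Appendix 9 has them recorded under the alternative AE or SAE, which may carry a non-hepatic preferred term. If the explanation is not an AE, it is recorded only on the appropriate CRF. SAP 3.8.2 tabulates AESIs by system organ class and preferred term, so neither route clearly leads to the hepatic AESI table.

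6. **What SAP 3.8.4 covers.** Its summaries ignore cause but are defined for each laboratory parameter. They do not show how many subjects had both elevations together.

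**Illustration only.** Take 143 per arm (SAP 2.4). Assume a share *r* of subjects meets the laboratory criterion and a share *s* of those is judged to have no other cause. Neither value is in the documents. The laboratory count is 143 × *r*; the Hy's Law count is 143 × *r* × *s*.

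| *r* (assumed) | 143 × *r* | *s* = 0% | *s* = 10% | *s* = 50% | *s* = 100% |
|---|---|---|---|---|---|
| 2% | 2.9 | 0 | 0.3 | 1.4 | 2.9 |
| 5% | 7.2 | 0 | 0.7 | 3.6 | 7.2 |
| 10% | 14.3 | 0 | 1.4 | 7.2 | 14.3 |

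If the true rates were 5% on placebo and 10% on MEDI3902, the laboratory counts would differ by 14.3 − 7.15 = 7.15 subjects. With the same *s* in both arms, the Hy's Law counts would differ by 7.15 × *s*: about 0.7 at *s* = 10%, and anything from 0 to 7.15 over the full range.

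**The case against.** The strongest counter-argument is that 5.3.1 does not cite Appendix 9, and that the analysis wording in Protocol 4.8.4.1 and SAP 3.8.2 is not limited to confirmed Hy's Law, so the narrow reading is not forced. This stands in part: it shows that the tabulated set is unsettled. It does not make the definition sound, because Protocol 5.6.3 refers to Appendix 9 for evaluating Hy's law and no other readable section defines it.

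Several other points also stand:

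- SAP 3.8.4 compares each liver test by arm regardless of cause, so an excess in ALT, AST or bilirubin alone could be seen.
- Protocol 4.8.4.1 says safety rests primarily on TEAEs and TESAEs, and explained cases that are AEs remain in those tables.
- SAP section 1 leaves table details to a separate programming plan that is not available here. The absence of a combined table can be stated only for the readable SAP.
- An AESI confined to drug-attributed cases suits rapid safety reporting, which is one purpose Protocol 5.3 gives for AESIs.

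A reader might infer more than the text supports:

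- **That 5.4.3.1 counts a sepsis-explained case as an AESI while 5.3.1 does not.** Section 5.4.3.1 tells sites to record the diagnosis as an AE or SAE; it never says the event counts as an AESI.
- **That the count will be near zero in both arms.** No rates are given. Appendix 9 requires an agreed alternative explanation, not merely a plausible one, and if information is delayed beyond 3 weeks it assumes for the time being that there is none.
- **That the rule favours MEDI3902.** Attribution is made in a double-blind trial (Protocol 4.6.2). The expected harm is lost or inconsistently classified events rather than a directional error.

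**Conclusion.** The point holds as a gap in analysis and definition. Protocol 5.3.1, read with Appendix 9, makes the hepatic component of the primary safety endpoint depend on blinded causality opinion. The readable SAP has no by-arm comparison of combined elevation free of that opinion. Sections 5.3.1, 5.4.3.1 and Appendix 9, together with Protocol 4.8.4.1 and SAP 3.8.2, do not settle which events enter the AESI table.

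The size of the effect cannot be estimated from the documents; the illustrative counts only follow the assumed rates. The conclusion rests on reading Hy's law in 5.3.1 as Appendix 9 defines it. It does not show that the primary safety assessment as a whole fails, or that the AESI in 5.3.1 must be redefined: a table in the SAP gives the attribution-free comparison without that.

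**What to change.** 1. In SAP 3.8.2 or 3.8.4, add one table by treatment group in the As-treated population: number and percentage of subjects meeting the Appendix 9 Potential Hy's Law laboratory criterion after dosing, irrespective of cause. Show judged Hy's Law cases as a subset, and show separately the subjects who already met the criterion at baseline. State the time window and carry over the Appendix 9 rule on the order of the two elevations.

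2. Reconcile Protocol 5.3.1, 5.4.3.1 and Appendix 9 with SAP 3.8.2 on which events count as the hepatic AESI and under which reporting term. State the definition once, remove the circular reference, and clarify what the known-diagnosis branch is for.

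The cost is small. Protocol 4.3.4 already requires the liver tests to be done and assessed concurrently. Table 4.2.2-1 has chemistry predose and on Days 8 and 22, and Potential Hy's Law cases already go into liver CRF modules. No new data are needed. The downside is one more table, in which many cases will reflect critical illness. The table needs only a SAP change; the protocol wording would need an amendment under Protocol 7.5 if judged substantial.

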# 5.3.2 Hypersensitivity (Including Anaphylaxis) and Infusion related Reactions

Administration of polyclonal immunoglobulin preparations and mAbs have been associated with hypersensitivity (including anaphylaxis) and infusion related reactions that occur during or after dosing. A hypersensitivity reaction is defined as an acute onset of an illness with involvement of the skin, mucosal tissue, or both, during infusion of investigational product (but does not meet the definition of anaphylaxis). Anaphylaxis is an acute onset, potentially fatal, systemic allergic reaction that is distinct from simple allergic reactions (eg, rash, pruritus) because of the simultaneous involvement of several organ systems (Sampson et al, 2006). An infusion related reaction is defined as any other reaction (other than hypersensitivity or anaphylaxis) occurring during infusion of investigational product or felt to be temporally related to the infusion.

Anaphylaxis and infusion related reactions have some common manifestations and may be difficult to distinguish from each other. Infusion related reactions typically develop within

30 minutes to 2 hours after the initiation of first drug infusion. However, though less frequent, infusion related reactions can occur later on within first 24 hours from the start of infusion, and are less common following subsequent exposures. Infusion related reactions may manifest with single or multiple signs and symptoms. Most of them are mild in intensity, but severe and even fatal reactions have been reported. Unlike infusion related reaction, anaphylaxis is a rare event, usually occurring after subsequent exposure to antigen, and it is most commonly accompanied by severe systemic skin and/or mucosal reactions. A full definition of anaphylaxis is provided in Appendix 3.

Signs and symptoms of hypersensitivity (including anaphylaxis) and infusion related reactions include, but are not limited to, fever, chills, rigors, myalgia, weakness, flushing, sweating, headache, dizziness, lightheadedness, syncope, seizure, anxiety, nasal congestion, rhinitis, sneezing, oropharyngeal or laryngeal edema, bronchospasm, dyspnea, tachypnea, cyanosis, respiratory arrest, tachycardia, hypotension, arrhythmia, chest pain, ischemia or infarction, cardiac arrest, flushing, erythema, pruritus, urticaria, angioedema, maculopapular rash, nausea, vomiting, cramping, and diarrhea (Kang and Saif, 2007).

Infusion of biological products is commonly associated with infusion related reactions. Anaphylaxis and infusion related reactions have some common manifestations and may be difficult to distinguish from each other. Infusion related reactions are commonly observed during or shortly after the first time exposure to therapeutic mAbs delivered through IV infusion. These reactions are less common following subsequent exposures. Unlike infusion related reactions, anaphylaxis is a rare event, usually occurring after subsequent exposure to an antigen, and it is most commonly accompanied by severe systemic skin and or mucosal reactions. The investigator is advised to carefully examine symptoms of adverse reactions observed during or shortly after exposure to investigational product, and consider the above mentioned facts prior to making a final diagnosis. For the investigator's convenience and in order to facilitate consistency in judgments a copy of the National Institute of Allergy and Infectious Diseases (NIAID) and Food, Allergy and Anaphylaxis Network (FAAN) guidance for anaphylaxis diagnosis is provided in Appendix 3.

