# Appendix 3 National Institute of Allergy and Infectious Diseases and Food, Allergy and Anaphylaxis Network Guidance for Anaphylaxis Diagnosis

NIAID and FAAN define anaphylaxis as a serious allergic reaction that is rapid in onset and may cause death. They recognise 3 categories of anaphylaxis, with criteria designated to capture from 80% of cases (category 1) to > 95% of all cases of anaphylaxis (for all 3 categories).

1. Acute onset of an illness (minutes to several hours) with involvement of the skin, mucosal tissue, or both (eg, generalised hives, pruritus or flushing, swollen lips-tongue-uvula)

AND AT LEAST ONE OF THE FOLLOWING

- a. Respiratory compromise (eg, dyspnea, wheeze-bronchospasm, stridor, reduced peak expiratory flow [PEF], hypoxemia)
- b. Reduced blood pressure (BP) or associated symptoms of end-organ dysfunction (eg, hypotonia [collapse], syncope, incontinence)
- 2. Two or more of the following that occur rapidly after exposure to a likely allergen for that patient (minutes to several hours):
  - a. Involvement of the skin-mucosal tissue (eg, generalised hives, itch-flush, swollen lips-tongue-uvula)
  - b. Respiratory compromise (eg, dyspnea, wheeze-bronchospasm, stridor, reduced PEF, hypoxemia)
  - c. Reduced BP or associated symptoms (eg, hypotonia [collapse], syncope, incontinence)
  - d. Persistent gastrointestinal symptoms (eg, crampy abdominal pain, vomiting)
- 3. Reduced BP after exposure to known allergen for that patient (minutes to several hours):
  - a. Infants and children: low systolic BP (age specific) or greater than 30% decrease in systolic BP
  - b. Adults: systolic BP of less than 90 mm Hg or greater than 30% decrease from that person's baseline

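### Non-anaphylactic hypersensitivity is defined by onset during the infusion only, so later skin or mucosal reactions are counted as infusion related reactions or, in a narrow group, fall outside the AESIs

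*Protocol*

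**What the plan says.** Protocol Section 5.3.2 introduces the risk as "hypersensitivity (including anaphylaxis) and infusion related reactions that occur during or after dosing". The next sentence defines a hypersensitivity reaction as an acute illness with "involvement of the skin, mucosal tissue, or both, during infusion of investigational product (but does not meet the definition of anaphylaxis".

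An infusion related reaction is any reaction, other than those two, "occurring during infusion of investigational product or felt to be temporally related to the infusion". The section adds that "infusion related reactions can occur later on within first 24 hours from the start of infusion". Appendix 3 does not tie anaphylaxis to the infusion; its first category begins "Acute onset of an illness (minutes to several hours) with involvement of the skin, mucosal tissue, or both".

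For analysis, Protocol Section 4.8.4.1 names "hypersensitivity reactions (including anaphylaxis), infusion related reactions, and" immune complex disease among the AESIs, alongside hepatic abnormalities. SAP 3.8.2 plans a table of duration and "time to onset from dosing start for AESIs including hypersensitivity reactions", infusion related reactions and anaphylactic reactions.

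On the collection window, Protocol Section 5.4.1 records AESIs from informed consent to 49 days after the dose. Section 5.4.3 starts collection just after the product has been given. Table 4.2.2-1 marks AESIs in the predose and dose columns of Day 1 as well as afterwards.

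**The concern.** Two consecutive sentences of Section 5.3.2 give different windows for the same event. The first covers the time after dosing and the definition does not. Sites will classify by the definition, so the label given to a skin or mucosal reaction depends on when the pump stopped and not on what the reaction was.

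The categories are named separately in the analysis plan, so the label matters. A low hypersensitivity count could partly be a product of the definition, and an onset table with no late hypersensitivity could not show whether late cases occurred. The AESI label also matters during the trial. Section 5.3 gives rapid reporting as a purpose of the label, and Section 3.1.3 has the data monitoring committee follow the rate of infusion or allergic reactions.

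**Working it through.** The point turns on definitions, and the plan has no figure of its own to reproduce. Side by side:

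| AESI category | Where defined | Limit on onset |
|---|---|---|
| Hypersensitivity, not anaphylaxis | Protocol 5.3.2 | During the infusion |
| Anaphylaxis | Protocol 5.3.2, Appendix 3 | Minutes to several hours; not tied to the infusion |
| Infusion related reaction | Protocol 5.3.2 | During the infusion, or judged related to it in time; onset described up to 24 hours from the start |
| Immune complex disease | Protocol 5.3.3 | Not tied to the infusion; serum sickness typically at 1 to 2 weeks |

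Only the first row ends with the infusion.

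**Sorting a skin or mucosal reaction that starts after the infusion ends**

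1. It meets the anaphylaxis criteria: it is still an AESI, and Section 4.8.4.1 groups anaphylaxis with hypersensitivity.
2. It is not anaphylaxis but is judged related in time: it becomes an infusion related reaction. It is relabelled but remains an AESI.
3. It is a serum sickness type of rash: it is immune complex disease, also an AESI.
4. It is none of these: it has no AESI category. It is still a treatment-emergent adverse event, or a serious one if it meets those criteria.

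**Length of the mismatch**

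Section 4.6.1 limits the infusion to 8 hours, or 12 hours after a dose adjustment. Measured against the 24 hours that Section 5.3.2 describes for infusion related reactions:

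- 24 − 8 = 16 hours
- 24 − 12 = 12 hours

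So for at least 16 hours (12 hours after a dose adjustment) an acute skin reaction can be an infusion related reaction but not non-anaphylactic hypersensitivity. A shorter infusion lengthens this period. These are clock hours, not shares of cases. The cut-off also varies between subjects, because Section 3.1.3 allows an infusion to be stopped, reassessed in about 30 to 60 minutes and restarted more slowly.

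**Collection window**

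Read literally, Section 5.4.3 begins when administration is over, while the hypersensitivity definition ends at that moment. The two windows do not overlap. Section 5.4.1 and Table 4.2.2-1 show that a wider window was intended.

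**The case against.** A reader might infer that post-infusion reactions are lost from the primary safety endpoint. The documents do not support that. Under Protocol Section 2.2.1 the endpoint comprises all treatment-emergent adverse events, serious events and AESIs through 49 days. Section 5.1 makes any adverse event after first receipt of product treatment-emergent, and SAP 3.8.1 tabulates all of them by system organ class and preferred term. Urticaria after the infusion, or a rash on day 10, is counted.

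A reader might also infer that nothing starting after the infusion can be classed as hypersensitivity. That is wrong for anaphylaxis. Nor does the short infusion, set against 49 days of follow-up, measure what is missed. Section 5.3.2 says that infusion related reactions typically begin 30 minutes to 2 hours after the start, so risk is not spread evenly over the 49 days.

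The rest of the case against is that little changes in practice. Most affected acute events remain AESIs as infusion related reactions and appear in the same SAP 3.8.2 table with their onset times. Serum sickness is covered. SAP 3.8.2 lets the Medical Monitor add groupings. The definition is the same in both blinded arms and does not by itself favour either.

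All of this stands, and it limits the point to classification. It does not remove the contradiction in Section 5.3.2. An equal definition in both arms also does not protect the hypersensitivity row: if the antibody causes reactions that start after the infusion, the excess shows up under infusion related reactions. On Section 5.4.3, a site would probably read the start loosely, since that section itself points to Table 4.2.2-1. The text still needs to agree with Section 5.4.1.

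**Conclusion.** The point holds as a misclassification between AESI categories, with a narrow group dropped from the AESI component. The count of non-anaphylactic hypersensitivity and its time-to-onset summary are cut off at the end of infusion, and the infusion related reaction count is raised by the cases that move. The number of cases is unknown, and would be zero if no such reaction began after the infusion. The total of treatment-emergent events is unaffected, and the count of subjects with any AESI changes only through the narrow group.

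This rests on two assumptions: that sites apply the Section 5.3.2 definition as written, and that the tables keep hypersensitivity and infusion related reactions apart, as both documents name them. It does not threaten the trial, but it should be corrected because the rule as stated produces the wrong label.

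**What to change.** - **Protocol 5.3.2:** define a hypersensitivity reaction as an acute skin and/or mucosal reaction, short of anaphylaxis, with onset during or after the infusion and within 24 hours of its start. Section 5.3.2 already mentions that limit for infusion related reactions. State that this category takes precedence. The infusion related reaction definition is already residual, so it can stand.
- **Protocol 5.4.3:** align the start of AESI collection with Section 5.4.1 and Table 4.2.2-1.
- **SAP 3.8.2:** apply the same rule in the AESI and time-to-onset tables.

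No new AESI category is needed. Infusion related reactions need not exclude skin signs, since the sign list in Section 5.3.2 is shared by these reaction types. After the change, an isolated skin reaction beyond 24 hours that is neither judged related in time nor immune complex disease would still be reported only as a treatment-emergent event; the text should say so.

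The cost is small. Adverse events are already collected through 49 days and time to onset is already planned. The sponsor should confirm that onset is captured by clock time around dosing, which the documents do not show. The downside is that a few events move between AESI rows.
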